### 8.3 Study procedures

Procedures which are part of the standard medical treatment are summarized in paragraphs 8.3.1-8.3.9. Measurements which are specifically measured for this study are listed in paragraph 8.3.10. A study flow chart is shown in figure 1. A treatment summary table, including an overview of what is and is not part of standard of care, is shown in table 1.

**Figure 1: Study flow chart**

**Table 1 Study parameter summary table**

	Baseline	End of RT	Months post (f)SRT								
			3M	6M	9M	12M	15M	18M	21M	24M	
Standard clinical care:											
Clinical characteristics: year of birth, gender, primary tumor type, presence of extracranial visceral metastases, primary tumor control, date diagnosis primary tumor, type of systemic therapy	X										
Coded data (see paragraph 12.1): patient number in electronic patient dossier											
Planning MRI & CT: number of brain metastases, total volume of brain metastases, volume of largest brain metastases	X										
Treatment characteristics: GTV largest metastasis, PTV largest metastasis, total volume GTV of all metastases, and total volume PTV of all metastases. Maximum dose in the PTV in anymetastasis. Maximum dose brain stem, chiasm, and optic nerves		X									
Physical examination	X										
WHO-PS and/or KPS	X										
Standard follow-up:											
Follow-up MRI: adverse local event (either radionecrosis or local failure according to RANO), distant brain recurrences			X	X	X	X	X	X	X	X	
Toxicity (CTCAE v5.0)			X	X	X	X	X	X	X	X	
Not part of standard follow-up:											
HRQoL (EORTC QLQ-C30, QLQ-BN20)	X		X	X		X		X		X	
IADL ( EQ-5D 5L)	X		X	X		X		X		X	
Other follow-up:											
Use of dexamethasone or bevacizumab	X		X	X	X	X	X	X	X	X	
Use of AED	X		X	X	X	X	X	X	X	X	
Salvage treatment, type of salvage treatment, date of salvage treatment						X					X
Alive/dead			X	X	X	X	X	X	X	X	
Symptomatic radionecrosis or local failure			X	X	X	X	X	X	X	X	

### 8.3.1 MR imaging before SRT

The definitive number of brain metastases and the definitive maximum lesion diameter any direction of the largest brain metastasis is determined on contrast-enhanced (single - triple dose Gd is allowed) T1-sequences, maximum slice thickness 1.5 mm, field strength (1.0-3.0 Tesla with a 3D-distortion correction protocol.

### 8.3.2 Cessation of systemic treatments during SRT

The combination of SRT with several systemic cancer treatments, namely gemcitabine, erlotinib, vemurafenib and trastuzumab-emtansine, has been reported to increase the risk of radionecrosis. Therefore, these systemic treatments are halted at least one week before the first fraction until at least one week after the last fraction. Immunotherapy can be continued during SRT. All other systemic treatments are halted at least three days before the first fraction until at least three days after the last fraction. All the above is in accordance with the Dutch guidelines for treatment of brain metastases

([https://richtlijnendatabase.nl/richtlijn/hersenmetastasen/startpagina\\_hersenmetastasen.html](https://richtlijnendatabase.nl/richtlijn/hersenmetastasen/startpagina_hersenmetastasen.html)).

### 8.3.3 Fractionation schedule and radiation dose before SRT

Patients randomized into the experimental fSRT cohort receive a fractionation schedule based on "Working Agreement for uniform dose prescription stereotactic (LINAC) irradiation of brain metastases, Dutch Platform of Neuro Oncology". This is 35 Gy in five fractions, or 30 Gy in five fractions if the metastasis is situated in the brainstem.

Patients randomized into the standard cohort will receive a fractionation schedule based on "Working Agreement for uniform dose prescription stereotactic (LINAC) irradiation of brain metastases, Dutch Platform of Neuro Oncology". This is in the range of 15 Gy in a single fraction up to a 24 Gy in three fractions.

The dose gradient outside the PTV will be as steep as possible to spare healthy brain tissue. Within the PTV there will be considerable dose inhomogeneity

*Dose prescription to brain metastases*

PTV of brain metastases	Dose 1 fraction	BM in brainstem (GTV=PTV)	Dose 5 fractions (Gy)	BM in brainstem (GTV=PTV)
<1 cm 	24	16	35	30
1-10 cm 	21	16	35	30
10-20 cm 	18	16	35	30
20-65 cm 	15 or 3X8Gy	No SRS	35	30

### Organ at risk constraints

	1 fraction (Gy) Optimal	1 fraction (Gy) Mandatory	D max 3 fractions (Gy) Optimal	D max 3 fractions (Gy) Mandatory	D max 5 fractions (Gy) Optimal	D max 5 fractions (Gy) Mandatory
Brainstem D max	10	18	24	27	23	30
Cochlea D mean	4	9	17	20	22	25
Chiasm D max	8	10	15	23	20	25
Lens D max	1	3	2	4	3	5
Optic nerves D max	8	10	15	23	22	25
Pituary gland D mean	8	10	15	23	22	25

### Acceptable and unacceptable variation in dose

Volume	Per protocol D (Gy)	Acceptable variation	Unacceptable variation
PTV	V 100% = 99%	98% < V 100% < 99%	V 100% < 98%
D max OAR if volume of OAR < 2 cm 	0.035 cm 	D 0.035cm3 ≤ D max	D 0.035cc > D max
D max OAR if volume of OAR ≥ 2 cm 	2%	D 2% ≤ D max	D 2% > D max

### 8.3.4 GTV and OARs

The GTV is defined by contouring the outer contrast-enhancing border of the brain metastasis on a T1 Gd weighted MRI scan. Brain metastases are named GTV1, GTV2, GTV3, etc. from cranial to caudal. OARs (brainstem, optic nerves, chiasm, pituitary gland, etc.) are contoured according to EPTN consensus.

### 8.3.5 SRT PTV

The PTV is defined by a 0-2 mm isotropic expansion of the GTV, according to institutional standards for SRT. If a brain metastasis is within or adjacent to the brainstem, the PTV margin will be 0 mm. If in an institution a smaller GTV to PTV margin is used when lesions are treated using multiple isocenters, then this technique is to be considered to reduce the V12Gy of the largest brain metastasis if it would otherwise be more than 10 cm^3.

### 8.3.6 SRT planning procedure

Patients will be immobilized in supine position wearing a thermoplastic mask or stereotactic non-invasive frame, with or without bite block and/or other fixation, according to institutional standards for SRT. The accuracy of the stereotactic fixation system should be sufficient to justify the CTV to PTV margin used. This means the intrafraction motion should at least be within the CTV-PTV margin used. If a margin of 0 mm is used, the maximum intrafraction motion should be <0.5 mm, with the SD being less than 0.25 mm. A planning CT scan with

≤2 mm thick contiguous slices (preferable CT slice thickness = 1mm) will be fused to a contrast-enhanced stereotactic MRI scan. The interval between the planning-MRI and actual SRT treatment is a maximum of 3 weeks.

### **8.3.7 SRT treatment technique**

Single or multiple isocenters are allowed for delivering SRT according to the treating center preference. Tissue density inhomogeneity correction will be used. Positional verification and correction prior to (and/or during) radiation should be executed according to the institutional protocol for stereotactic radiotherapy and should be in accordance with the CTV-PTV margin used. All techniques that result in the dose requirements being met are allowed. Participating institutes will have to define their radiation delivery treatment prior to the initiation of the study. Techniques that have a shorter treatment time duration are preferred as this is more comfortable for the patient and might prevent an increase of the intrafraction displacement over the treatment time.

### **8.3.8 Dose reporting SRT**

Tumor volume and treatment plan characteristics are reported (maximum dose, prescribed dose, and dose in critical organs at risk).

### **8.3.9 MR imaging after SRT**

Tumor response evaluation as well as presence of distant brain recurrences are monitored every three months after SRT on contrast-enhanced (single - triple dose Gd is allowed) T1-sequences, maximum slice thickness 3 mm, field strength (1.0-3.0 Tesla with a 3D-distortion correction protocol including perfusion MR).

### **8.3.10 Questionnaires and other measurements**

The following facultative questionnaires will be assessed at baseline, 3 months, 6 months, and 12 months, 18 months and 24 months after SRT: HRQoL (measured with EORTC QLQ-C30 and QLQ-BN20) and IADL (measured with EQ-5D 5L).

Toxicity (according to CTCAE v5.0) and use of AED, dexamethasone and bevacizumab is evaluated at baseline, 3 months after SRT and thereafter every three months until 2 years via telephone or during scheduled outpatient clinic visits. Need for salvage treatments, or symptomatic radionecrosis, and survival are all evaluated 2 years after SRT.

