#### 8.1.2 Secondary study parameters/endpoints

- Survival time/survival at 2 years post-SRT
- Incidence of symptomatic radionecrosis
- Incidence of symptomatic local failure
- Incidence of salvage treatments at 2 years post-SRT
- Distant brain recurrences at 2 years post-SRT
- Dose dexamethasone at baseline, 3 months after radiotherapy and thereafter every three months until 2 years
- Anti-epileptic drug (AED) use
- Bevacizumab use
- Grade 2 or more toxicity (CTCAE v5.0)
  - Alopecia, cognitive symptoms, fatigue, dysphasia, hearing loss, visual impairment, generalized muscle weakness

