### 9.2 AEs, SAEs and SUSARs

#### 9.2.1 Adverse events (AEs)

Adverse events are defined as any undesirable experience occurring to a subject during the study, whether or not considered related to the experimental intervention. All adverse events reported spontaneously by the subject or observed by the investigator or his staff will be recorded in the medical record of the patient.

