#### 9.2.2 Serious adverse events (SAEs)

A serious adverse event is any untoward medical occurrence or effect that

- results in death;
- is life threatening (at the time of the event);
- requires hospitalization or prolongation of existing inpatients' hospitalization;
- results in persistent or significant disability or incapacity;
- is a congenital anomaly or birth defect; or
- any other important medical event that did not result in any of the outcomes listed above due to medical or surgical intervention but could have been based upon appropriate judgement by the investigator.

An elective hospital admission will not be considered as a serious adverse event.

The investigator shall report serious adverse events to [[contact]](mailto:[contact]) without undue delay after obtaining knowledge of the events, unless, for certain serious adverse events, the protocol provides that no immediate reporting is required.

Adverse experiences of a serious and unexpected nature, whether or not related to the cerebral radiotherapy, must be reported immediately. Adverse events that are

unexpected, should be reported if there is a possibility that it could be related to the administration of the radiotherapy.

The investigator will report all SAEs to the sponsor without undue delay after obtaining knowledge of the events, except for the following SAEs: epilepsy, deterioration of existing neurologic impairment after the radiotherapy, alopecia, fatigue, headache, and taste disorders.

The sponsor will report the unexpected SAEs through the web portal *ToetsingOnline* to the accredited METC that approved the protocol, within 7 days of first knowledge for SAEs that result in death or are life threatening followed by a period of maximum of 8 days to complete the initial preliminary report. All other unexpected SAEs will be reported within a period of maximum 15 days after the sponsor has first knowledge of the serious adverse events.

Patients with brain metastases generally have a poor life expectancy of around 3-12 months. Therefore, a significant proportion of patients is expected to die within the study duration of 1 year after SRT.

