### **9.5 Data Safety Monitoring Board (DSMB) / Safety Committee**

The establishment of a Data Safety Monitoring Board or Safety Committee is not deemed necessary for this study. The study aims to investigate a potentially safer treatment method than the current standard of care. It is unlikely that the risk of adverse events will be increased in the experimental cohort compared to the standard cohort. The only difference between the two cohorts is the fractionation schedule. The only difference is expected in the rate of local control and radionecrosis, which constitutes the primary study endpoint.

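### No CTCAE toxicity assessment is scheduled between the start of radiotherapy and month 3, and the protocol states no look-back or chart route that brings earlier events into the grade 2+ comparison

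*Protocol*

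**What the plan says.** Section 8.1.2 lists grade 2 or higher CTCAE v5.0 toxicity as a secondary endpoint and names seven terms: "Alopecia, cognitive symptoms, fatigue, dysphasia, hearing loss, visual impairment, generalized muscle weakness". It gives no time window, no worst-grade rule and no rule for patients who die before an assessment.

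Section 8.3.10 sets the timing: toxicity "is evaluated at baseline, 3 months after SRT and thereafter every three months until 2 years", by telephone or at an outpatient visit. Table 1 marks toxicity from 3 to 24 months. The table has an End of RT column, but it is empty for toxicity.

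Outside this schedule, section 9.2.1 says that adverse events "reported spontaneously by the subject or observed by the investigator or his staff will be recorded in the medical record of the patient". Section 9.2.2 has serious adverse events reported to the sponsor, with a list of exceptions that includes alopecia and fatigue; expected serious events are line-listed every half year. For patients who withdraw after randomisation, section 8.6 seeks permission to consult the chart only for how they were treated and how long they lived. Section 8.4 applies the same rules to patients who become incapacitated and can no longer be assessed.

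On prognosis, section 9.2.2 states: "Patients with brain metastases generally have a poor life expectancy of around 3-12 months".

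**The concern.** The first scheduled look at toxicity comes three months after treatment, in a population that the protocol itself expects to have short survival. An event that begins and resolves before that contact reaches the endpoint only if the month-3 assessment looks back, and the protocol does not say that it does. Centres could fill in the same form differently, some grading current status and others the worst grade over the interval.

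For a patient who dies or withdraws before month 3, even a look-back does not help, because no contact takes place. The grade 2+ comparison would then describe mainly patients who reached month 3.

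This also bears on how the trial can support its own expectation about safety. In explaining why no monitoring board is needed, section 9.5 says: "It is unlikely that the risk of adverse events will be increased in the experimental cohort compared to the standard cohort". For non-serious toxicity in the first three months, the plan schedules no collection that would show whether this held. Incidental chart notes are a weak substitute, since one arm attends for five fractions and the other for one or three, so the chances to mention a symptom differ by arm.

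**Working it through.** **Step 1. Is anything scheduled before month 3?**

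| Source | Baseline | End of RT | Month 3 | Later |
|---|---|---|---|---|
| Section 8.3.10 (text) | yes | not mentioned | yes | every 3 months to 2 years |
| Table 1, toxicity row | empty | empty | marked | marked every 3 months to month 24 |

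Text and table differ on baseline but agree on the point at issue: no assessment falls between the start of treatment and month 3.

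**Step 2. Does another stated route fill the gap?**

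- Section 9.2.1 (all adverse events): kept in the medical record, with no CTCAE grade required and no link to the endpoint.
- Section 9.2.2 (serious events): reported, but many grade 2 events would not meet the seriousness definition. Alopecia and fatigue, two of the seven endpoint terms, are exempt from prompt reporting even when serious.
- Section 8.6 (withdrawals): the chart permission does not cover toxicity.
- Deaths before month 3: no rule.

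So no route into the grade 2+ endpoint is stated for non-serious events in patients who never reach month 3. For those who do reach it, the route depends on an undefined reference period.

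**Step 3. How many patients could this affect?** The protocol gives no figure for deaths before month 3, so there is none to reproduce. Inputs:

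- Life expectancy of about 3-12 months (section 9.2.2). Reading it as a median is an assumption.
- Exponential survival, also an assumption.
- Planned total of 130 with 1:1 allocation (section 4.4): 130 / 2 = 65 per arm.

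With median m in months, the share dead by month 3 is 1 − 0.5^(3/m).

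| Median m | Calculation | Share | Of 130 | Of 65 per arm |
|---|---|---|---|---|
| 3 | 1 − 0.5^1 | 50% | 65 | 32.5 |
| 6 | 1 − 0.5^0.5 | 29% | 38 | 19 |
| 9 | 1 − 0.5^(1/3) | 21% | 27 | 13 |
| 12 | 1 − 0.5^0.25 | 16% | 21 | 10 |

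The life expectancy is stated for patients with brain metastases in general. Section 4.2 admits only those with KPS of at least 70 who are suitable for SRT, which points towards the last row. Withdrawals before month 3 would add to these counts; the protocol gives no rate for them.

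**The case against.** **The month-3 assessment may already look back.** The protocol says that toxicity is evaluated at that contact and does not limit this to symptoms then present. This stands. A reader might infer that early toxicity is never graded and never enters the comparison; the text does not support that. It supports only that the reference period is unstated.

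**A recall window and the counting of early deaths belong in the form instructions or the statistical analysis plan.** This has force for the recall window taken alone. It does not cover patients who die or withdraw before any contact, because an analysis plan cannot recover grades that nobody was asked to collect.

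**Early harm is captured elsewhere.** In part it is: serious events are reported or line-listed, unexpected ones go to the ethics committee on short deadlines, and section 9.1 provides for a safety halt. A reader might infer that the trial has no view of acute safety, or that the decision against a monitoring board rests on this endpoint. Neither follows. Section 9.5 argues from the expected effect of fractionation, and the gap concerns non-serious toxicity.

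**The protocol expects the arms to differ in local control and radionecrosis, not acutely, and three-monthly toxicity checks follow usual care.** This is fair. Nothing in the protocol shows that an acute difference is likely, and the schedule may be a deliberate low-burden choice. Grade 2+ toxicity is nevertheless a named endpoint, with terms such as fatigue and alopecia that are not confined to late effects.

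**The size is uncertain, and no bias is shown.** Both parts stand. The 50% figure needs a median of 3 months, which suits the enrolled population poorly. Nothing shows that early deaths will differ between randomised arms, so what is shown is lost information and not a biased comparison.

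**Section 10.2 promises continued follow-up of patients who withdraw.** That is a general intention. Section 8.6, which says what is actually asked of them, does not include toxicity.

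**Conclusion.** The point holds in limited form. No toxicity assessment is scheduled before month 3. The protocol gives the month-3 entry no look-back period, and it gives no route by which earlier non-serious events, or events in patients who die or withdraw before month 3, reach the grade 2+ comparison.

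Under the two survival assumptions, 16% to 50% of patients would die without a scheduled post-treatment grade; about 10 of 65 per arm is the more plausible end. The endpoint is secondary, and the primary analysis and sample size are untouched. The change is worth making because it concerns data capture and cannot be made after the fact.

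**What to change.** In section 8.3.10 and Table 1:

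- Define the month-3 entry as the worst CTCAE grade since the first fraction, and each later entry as the worst grade since the previous contact.
- For patients who die before month 3, complete the same form from the medical record.
- For patients who withdraw before month 3, do the same only if the chart permission in section 8.6 is extended to toxicity.
- Report grade 2+ toxicity on these worst grades by randomised arm, and show per arm how many patients were graded from charts.
- In the same edit, reconcile the baseline toxicity entry, which the text includes and the table leaves blank.

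The cost is a changed recall window on an existing form, one chart check per early death or permitted withdrawal, and a small change to the consent wording. No extra visit or call is needed. There are two limitations. Patients must recall up to three months. Chart-based grades will be less complete and may differ by arm because the arms attend a different number of times, which is why the chart-graded count should be shown per arm.

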## **8.4 Withdrawal of individual subjects**

Subjects can leave the study at any time for any reason if they wish to do so without any consequences. The investigator can decide to withdraw a subject from the study for urgent medical reasons.

If a subject becomes incapacitated during the study period, and if it will no longer be possible to make MRI scans, to send questionnaires, to evaluate toxicity, etc. In such a case, the same guidelines are followed as described for subjects who withdraw from the study for any reason (see 8.5 and 8.6).

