As clinicians, we observe an increasing number of long term survivors over several years with brain metastases. Brain necrosis or radionecrosis is a long term side effect of SRT which occurs in +/-20% of patients and the incidence may increase up to +/-40% if SRT is combined with immunotherapy. Radionecrosis may cause neurologic symptoms, such as focal neurological deficits, neurocognitive dysfunction and seizures, which require treatment with steroids, bevacizumab, or sometimes even surgery. SRT is mostly delivered with an ablative high radiotherapy dose in a single fraction. In the first millimeters close to the brain metastasis, the healthy brain tissue receives a high dose as well.

In radiotherapy literature, it is known that more fractionated radiotherapy, e.g. hypofractionated radiotherapy (fSRT), may decrease side effects. fSRT means delivering the ablative dose in multiple fractions (f.e. 5 fractions) over several days instead of delivering the ablative dose within half an hour. Recent retrospective studies showed that risk difference of local failure and radionecrosis is almost 30% in larger tumors (>2.5 cm; constituting around

50% of metastases), while the incidence is equivalent in smaller metastases. To achieve a local control of more than 90% after one year, it is important to deliver a cumulative biologically effective dose (BED) of at least 50 Gy. 35 Gy in 5 fractions results in a BED of more than 50Gy. Another potential benefit of fSRT over SRT in one or three fractions is better induction of an abscopal effect. SRT in one or three fractions results in massive tumor necrosis. fSRT may result in more regulated cell death: apoptosis, with better antigen presentation of dying tumor cells. It is hypothesized that this may subsequently result in better activation of the immune cells against the cancer and better control of micrometastases outside the irradiation field. Several studies are ongoing in which SRT is combined with immunotherapy to increase systemic tumor control and thereby improve survival.

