### **8.5 Replacement of individual subjects after withdrawal**

With respect to patients applicable for this study willing to participate, and who have signed informed consent (paragraph 11.2): before randomization any patient will be replaced if the patient withdraws for any reason. These patients are not included in the statistical analysis. After the randomization, patients withdrawing for any reason will not be substituted by additional patients and these patients are analyzed by intention to treat.

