### **8.6 Follow-up of subjects withdrawn from treatment**

Patients who withdraw after randomization will not be requested to participate for follow-up questionnaires. Patients are asked if it is allowed to consult their medical chart for treatment characteristics and survival length.

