Expected SAEs are hospitalization or death by progression of both extracranial and intracranial cancer. Moreover, patients are treated with systemic therapy, and may be hospitalized or die because of complications of the systemic therapy, such as secondary infections. Furthermore, a proportion of patient will have severe neurologic impairment and epilepsy, because of intracranial cancer progression despite radiotherapy. These expected SAEs will be reported every half year in a line listing.

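### Incapacitated patients who can no longer be assessed follow the withdrawal route, where chart review covers only treatment characteristics and survival, so outcome data already in the record can be lost for reasons linked to the outcome

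*Protocol*

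**What the plan says.** Section 8.4 sets a two-part condition: "If a subject becomes incapacitated during the study period, and if it will no longer be possible to make MRI scans", with questionnaires and toxicity evaluation named alongside MRI. For such patients "the same guidelines are followed as described for subjects who withdraw from the study for any reason", with a reference to 8.5 and 8.6.

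Under 8.5, after randomisation "patients withdrawing for any reason will not be substituted by additional patients and these patients are analyzed by intention to treat". Under 8.6, "Patients who withdraw after randomization will not be requested to participate for follow-up questionnaires", and "Patients are asked if it is allowed to consult their medical chart for treatment characteristics and survival length". No other data item is listed.

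Section 10.2 points the other way. It undertakes to limit missing data and to go on following patients who withdraw.

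On the link between outcome and incapacity, section 1 says "Radionecrosis may cause neurologic symptoms, such as focal neurological deficits, neurocognitive dysfunction and seizures". Section 9.2.2 expects that "a proportion of patient will have severe neurologic impairment and epilepsy, because of intracranial cancer progression despite radiotherapy".

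**The concern.** A patient who loses capacity has not chosen to leave the study. Among the possible causes are radionecrosis and local failure, the two components of the primary endpoint. A rule that narrows data collection at that moment can remove information because of the outcome the trial measures.

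The narrowing is also wider than the inability to assess requires. New study assessments may be impossible while the hospital record still holds a standard-care scan, a multidisciplinary board diagnosis, a salvage procedure, or steroid and bevacizumab prescriptions. Section 8.6 does not provide for reading any of these. This is a rule about which data are collected, so an analysis plan could not repair it afterwards.

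At stake are the secondary endpoints on symptomatic radionecrosis, symptomatic local failure, salvage and drug use, which could lose some of their most severe cases. To a lesser extent the primary difference could shrink, since a loss proportional to events removes more of them from the arm that has more.

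**Working it through.** **Step 1. Which outcomes survive the withdrawal route?** Endpoints are from 8.1.1 and 8.1.2, and the permitted data are from 8.6.

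| Outcome | Can the record hold it without new study assessments? | Listed in 8.6? |
|---|---|---|
| Survival | Yes | Yes |
| ALE on a standard-care scan or diagnosed by the board, not yet captured | Yes | No |
| Symptomatic radionecrosis or local failure | Yes | No |
| Salvage treatment | Yes | No |
| Dexamethasone, bevacizumab, anti-epileptic use | Largely | No |
| CTCAE toxicity | In part only; 8.3.10 obtains it by telephone or clinic visit | No |
| New ALE with no further imaging | No | No |

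The last row matters. Section 8.1.1 defines both ALE components on MRI, so an event that is never imaged cannot be recovered by any wording of 8.4 or 8.6.

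**Step 2. Timing.** ALE status comes from three-monthly MRI (8.3.9, Table 1), so an ALE imaged before incapacity is already recorded. Section 8.3.10 places the evaluation of salvage need and symptomatic radionecrosis at 2 years, although Table 1 lists symptomatic events three-monthly. The secondary endpoints are therefore more exposed than the primary.

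**Step 3. Reproduce the stated power.** Inputs from section 4.4: 59 per arm, risks of 30% and 10% (stated there at 1 year), alpha 0.05, two-sided Z test with pooled variance, exact binomial results. For each pair of event counts (x, y),

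Z = (x/59 − y/59) / √[p(1 − p)(2/59)], with p = (x + y)/118.

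Summing the binomial probabilities of all pairs with |Z| ≥ 1.96 gives power 0.8051. At 10% in both arms it gives an actual alpha of 0.0507. Both match the protocol.

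**Step 4. Illustrate the effect on the primary comparison.** Assumption: a share f of ALEs, equal in both arms, is never recorded, and these patients are counted as event-free. The protocol gives no f, and 8.5 does not say what ALE status such patients carry. Recorded risks are 0.30(1 − f) and 0.10(1 − f). With equal arms the mean risk is 20%, so the patients affected are 0.20f of the total.

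| f | Recorded risks | Difference (points) | Patients affected | Exact power, 59 per arm |
|---|---|---|---|---|
| 0 | 30.0% v 10.0% | 20 | 0% | 0.805 |
| 5% | 28.5% v 9.5% | 19 | 1% | 0.779 |
| 10% | 27.0% v 9.0% | 18 | 2% | 0.751 |
| 20% | 24.0% v 8.0% | 16 | 4% | 0.686 |

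**Step 5. Vary the assumptions.** If lost cases are excluded instead, the risks become 0.30(1 − f)/(1 − 0.30f) and 0.10(1 − f)/(1 − 0.10f). The difference is then 27.8% − 9.1% = 18.7 points at f = 10%, and 25.5% − 8.2% = 17.4 points at f = 20%. A normal approximation, which gives 0.78 with no loss, puts power at 0.75 and 0.70.

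If all 130 planned patients (65 per arm) were evaluable, with no other missing data, exact power with lost cases counted as event-free would be 0.806 at f = 5% and 0.779 at f = 10%. The 10% allowance in 4.4 can offset lost numbers. It does not restore the shrunken difference.

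**The case against.** The strongest case against is that the loss comes mainly from being unable to scan, not from the withdrawal label. The rule applies only once MRI and the other assessments are impossible, and ALE is an MRI endpoint. Three-monthly imaging will already have recorded many events. Incapacity may also come from distant brain recurrence, which is a separate endpoint, or from extracranial disease or complications of systemic therapy. All of this stands. It confines the primary-endpoint effect to a subset whose size the protocol does not give.

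Three stronger readings are tempting, and the documents do not support them.

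- A reader might infer that any neurological decline ends follow-up. The condition in 8.4 is narrower. Chart review for survival continues with permission, 8.5 keeps these patients in the intention-to-treat analysis, and 10.2 promises continued follow-up.
- A reader might infer that chart access is impossible because an incapacitated patient cannot answer when, under 8.6, "Patients are asked if it is allowed to consult their medical chart". Section 11.2 already tells patients at consent that their records may be reviewed for trial purposes. The consent form is not at hand, so a gap in it cannot be asserted. What remains is that a second request, made after capacity is lost, is a poor fit for this group.
- A reader might take the power figures as an estimate of harm. They rest on an assumed loss share and an assumed handling of lost cases.

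The objection does not answer the omission in 8.6 of outcomes that are already in the record, nor the conflict between 8.6 and 10.2.

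**Conclusion.** The point holds in a limited form. Sections 8.4 and 8.6 together leave out of data collection outcomes that the hospital record may hold, in a group whose incapacity the protocol itself says can arise from radionecrosis or intracranial progression. Missingness can therefore depend on outcome. Section 8.6 also contradicts 10.2, and this affects every withdrawal, not only incapacity.

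The main consequence is for symptomatic events, salvage and drug use. For the primary endpoint the effect is limited to ALEs not recorded before incapacity, and its size cannot be derived from the document. If 5% to 20% of ALEs were lost equally in both arms and counted as event-free, power at 59 per arm would fall from 0.805 to between 0.779 and 0.686. A smaller loss would have a smaller effect. The change is worth making because it is inexpensive, not because serious bias has been shown.

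**What to change.** - **Section 8.4:** separate incapacity from voluntary withdrawal, and state that incapacitated patients remain on study for data collection from the record.
- **Section 8.6:** extend the permitted chart review, up to 2 years, to ALE status from any standard-care MRI or board diagnosis, symptomatic radionecrosis and local failure, salvage, dexamethasone, bevacizumab and anti-epileptic use, and vital status. Apply this to incapacitated patients and to withdrawing patients who agree.
- **Sections 8.6 and 10.2:** state one and the same rule for follow-up after withdrawal. Deleting the incapacity rule from 8.4 alone would leave this conflict in place.
- **Consent:** check that the form signed before randomisation covers this use of the record after loss of capacity, and add a line if it does not.

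The cost is some chart abstraction and ethics review of any added consent line. No extra visits or scans are needed, and treatment does not change. ALEs that are never imaged will still be missed.
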